3.6 Standardized procedures

Since our institute cares for anesthesia in up to 150 patients per year in bariatric surgery, we want to optimize the outcome and postoperative analgesia for patients and guarantee a phase free of pain and other complications. The intervention is usually proceeded laparoscopically, with an average length of 120 minutes. Overweight patients with a mean BMI of 38 points, receive general anesthesia (TIVA and initial fentanyl application of 0.6 - 1.0 mg I.V.). After completion of surgery, patients are transferred to PACU for further observation and treatment. Emphasizing, these patients require almost double amount of opiates in the perioperative setting, than patients receiving laparoscopic appendectomy or hemicolectomy, as well as during the postoperative phase. The adverse effects of an increased opiate consumption like nausea, vomiting, hypopnea, pruritus and reduced gastrointestinal function are commonly aggravating the symptoms of pre-existing diseases like sleep apnea syndrome, reduced functional residual capacity, due to higher intraabdominal mass and thereby caused dyspnoea. Based on increased pain levels, these patients receive up to 1.0 mg fentanyl during the first four hours after completion of surgery to cope with pain. Additionally, PONV, induced by opiates, presents a major discomfort for these patients.

4. STUDY OBJECTIVES

4.1 Primary study objective

To investigate if intravenous administration of lidocaine 1% I.V. in patients undergoing bariatric surgery reduces postoperative pain intensity within the first four hours after completion of surgery.

4.2 Secondary study objective

To investigate if the experienced average maximal pain intensity and the total opiate consumption of patients who underwent bariatric surgery can be reduced during the first four hours and 48 hours by perioperative lidocaine infusion.

4.3 Other objectives of interest

Other objectives of interest are as follows:

- Monitoring of PONV and its distribution between the groups.
- Comparing time to first defecation after completion of surgery in both groups in regard of a beneficial effect in the “lidocaine group”.
- Comparing length of hospitalization of both groups in regard of a beneficial effect in the “lidocaine group”.

5. STUDY OUTCOMES

5.1 Primary outcome

Any development of VAS/NRS score > 3 , in hourly measurements within the first four hours after completion of bariatric surgery.

5.2 Secondary outcome

Average experienced maximal pain during the first four hours and 48 hours (in hourly measurements on PACU and in eight-hourly measurements on surgical ward) is assessed by VAS/NRS score. The total amount of opiates (given during surgery and on PACU and administrated on surgical ward).

5.3 Other outcomes of interest

- any event of postoperative nausea and vomiting (subdivided by event of no nausea (PONV = 0), event of nausea without vomiting (PONV = 1) and event of nausea with vomiting (PONV = 2)) during first 48 hours after completion of surgery
- time to first defecation (quantified in hours)
- duration of hospitalization (quantified in days)

5.4 Safety outcomes

Vital parameters (blood pressure, pulse rate, oxygen saturation) will be recorded digitally by the electronic acute care patient data management system (ACPDMS) during the peri- and postoperative phase and according to institutional standards. Incidence of any potential adverse events (AE) requiring treatment attributable to lidocaine (e.g. local skin reactions, nausea, vomiting, dizziness, ear ringing, etc.), serious adverse events (SAE) (cardiac arrhythmia with relevant hemodynamic outcome, cardiac arrest) or adverse

events related to opiates (respiratory adverse events, ileus). Other outcomes of interest, precisely PONV will not be accounted for an AE.

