formed with lidocaine I.V. and studies described minor side effects like dizziness and „ear ringing“ after continuous infusion of 2 up to 6 mg/min lidocaine 2%. (52) Anyway, indication for systemic lidocaine needs to be strictly evaluated and, according to patients` risk potential for advert effects thoroughly selected. Contraindications for the application of systemic lidocaine comprise identified allergies to local anesthetics, a reduction in hepatic function as well as serious cardiac arrhythmias. First signs of intoxication occur after reaching plasma levels of 5 µg/ml and more. Based on their effect on voltage gated sodium channels, neurological and central nervous stimulation become apparent, followed by inotropic and bathmotropic effect-related cardiac failure. (42, 43) Based on anti-inflammatory effects, a higher susceptibility to infection has been discussed and has been confirmed in small investigations with rats. However, most studies showed a sufficient function of leucocytes and furthermore postulated anti-bacterial properties in vitro and in vivo. (44 - 46) Further information about expectation of adverse effects and safety reference information can be found in the prescribing information for lidocaine 1%, provided by Streuli Pharma. Obesity is a major factor for postoperative respiratory complications, especially in patients with confirmed or suspected obstructive sleep apnea (OSA). Increased risk of perioperative morbidity and mortality developes because of potential difficulty in maintaining patients` airway. Aggravation of OSA due to sedation, analgesia or extended effects and accumulation of narcotic agents, especially opiates, has been described. (53) Generally, regional analgesic techniques, like epidural analgesia should be considered to reduce or eliminate the requirement for systemic opiates, however difficulties in location and correct placement of epidural catheters can occure due to impeded anatomical proportions in obese patients. Practice guidelines for the management of patients with OSA, have been published by the American Society of Anesthesiologists, recommending well-considered use of sedatives and opiates for the peri- and postoperative course in this group of patients. (54) The application of lidocaine as an additional analgesia during bariatric surgery gives hope to reduce the before mentioned complications and adverse effects due to increased opiate consumption, to assure a postoperative phase more comfortable and less branded by side effects for the patient. Therefore, the study was designed to investigate if the proportion of patients suffering from higher pain intensity (any development of VAS/NRS score > 3, in hourly measurements) within first four hours after bariatric surgery can be reduced by preoperative lidocaine infusion. Secondary endpoints will include the total opiate consumption of patients,

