11. SAFETY ANALYSIS

11.1 Drug studies

During the entire duration of the study, all AE, ADR and all SAE, related to the application of IMPs (severity of possible AE related to lidocaine will be discussed in chapter 11.6) are collected, fully investigated and documented in source documents and case report forms (CRF). Study duration encompassed the time from when the participant signs the informed consent until study nurses final visit on second postoperative day at 2pm respectively +/- 30 minutes.

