11.2 Definition and assessment of (serious) adverse events and other safety related events

An AE is any untoward medical occurrence in a patient or a clinical investigation participant administered a pharmaceutical product and which does not necessarily have a causal relationship with the study procedure. An AE can therefore be any unfavourable and unintended sign (including an abnormal laboratory finding), symptom, or disease temporally associated with the use of a medicinal product, whether or not related to the medicinal product.

A **SAE** is classified as any untoward medical occurrence that:

- results in death
- is life-threatening
- requires in-patient hospitalization or prolongation of existing hospitalization
- results in persistent or significant disability/incapacity
- is a congenital anomaly/birth defect

In addition, important medical events that may not be immediately life-threatening or result in death, or require intensive care treatment, but may require intervention to prevent one of the other outcomes listed above should also usually be considered serious.

SAE should be followed until resolution or stabilization. Participants with ongoing SAE at study termination (including safety visit) will be further followed up until recovery or until stabilization of the disease after termination.

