11.6 Assessment of Severity

Severity of possible AE due to the application of IMPs will be classified as follows.

- Mild: numbness and tingling in the fingers and toes, numbness and unusual sensations around the mouth, a metallic taste in the mouth, ringing in the ears, or lightheadedness and dizziness, local skin reactions (redness, urticaria)
- Moderate: mild side effects with the addition of nausea and vomiting, severe dizziness, decreased hearing, tremors, changes in blood pressure and pulse

- Severe: drowsiness confusion, muscle twitching, convulsions, loss of consciousness, cardiac arrhythmias with hemodynamic instability, cardiac arrest

Events classified as severe adverse reactions due to IMPs will be included to the definition of SAE. Any other event, not applicable to the classification will be documented in the electronic anesthesia protocol and the CRF and assessed by the investigator if discontinuation and/or further treatment is required.

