11.9 Safety SOP

The Sponsor's standard operating procedures (SOP) provide more detail on safety reporting. During the entire duration of the study, all AE and all SAEs are collected, fully investigated and documented in source documents and CRF. Study duration encompassed the time from when the participant signs the informed consent until the last protocol-specific procedure has been completed, including a safety follow-up period.

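### Section 5.4 limits the non-serious lidocaine adverse-event outcome to events that are treated and attributed to lidocaine; the comparison between arms should count all adverse events, with these as subsets

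*Combined protocol and SAP*

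**What the plan says.** Section 5.4 lists vital parameters and then three kinds of event. The first is "Incidence of any potential adverse events (AE) requiring treatment attributable to lidocaine", with the examples "local skin reactions, nausea, vomiting, dizziness, ear ringing, etc". The second is "serious adverse events (SAE) (cardiac arrhythmia with relevant hemodynamic outcome, cardiac arrest". The third is adverse events related to opiates, illustrated by respiratory events and ileus. The section closes by saying that PONV is not counted as an adverse event.

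Other sections draw the line elsewhere:

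- Section 11.2 defines an adverse event as an occurrence "which does not necessarily have a causal relationship with the study procedure".
- Section 11.9 says that "all AE and all SAEs are collected, fully investigated and documented in source documents and CRF".
- Section 11.1 collects "all AE, ADR and all SAE, related to the application of IMPs".
- Section 11.6 sets a grade that begins "Mild: numbness and tingling in the fingers and toes, numbness and unusual sensations around the mouth, a metallic taste in the mouth" and goes on to ear ringing, light-headedness, dizziness and local skin reactions. It sets no condition about treatment.
- The study-sequence table in section 8.1 has AE, SAE and ADR recorded at every stage from surgery to the safety follow-up.

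Section 10.5 names generic tests for dichotomous and continuous data. It does not mention a safety table.

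**The concern.** In a blinded, placebo-controlled trial, the evidence that a drug causes an event is the difference in incidence between the randomised arms. Section 5.4 applies two conditions before an event enters that comparison: it was treated, and it was put down to lidocaine. The people who would make the attribution are blinded (section 6.4), and every patient also receives fentanyl, propofol and remifentanil (section 8.1). Dizziness in the PACU can reasonably be ascribed to any of these.

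The events most exposed to the two conditions are the early neurological signs. Section 3.5 says that lidocaine toxicity first shows in the nervous system, and it names dizziness and ear ringing as known minor effects. If such signs are recorded but not counted, the published incidence may rest on very few events, and a small difference would then say little about tolerability. Two analysts could also build different adverse-event tables, one from 5.4 and one from 11.9, and both could cite the protocol.

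**Working it through.** **1. Does an untreated mild sign count?** Take ear ringing that passes without treatment.

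| Section | Rule | Result |
|---|---|---|
| 11.2 | adverse event regardless of cause | is an adverse event |
| 11.6 | graded mild, no treatment condition | is graded |
| 11.9 and table in 8.1 | all adverse events recorded | is recorded |
| 5.4 | must be treated and attributable to lidocaine | not in the lidocaine adverse-event incidence |

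The event is in the database but outside the defined outcome. The same holds for a treated event that staff attribute to another drug, unless it falls under the serious or opiate-related components.

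**2. The plan's own figure.** The documents state no safety figure. The stated sample size is used here only to fix the denominator. Inputs from sections 10.2 and 10.3: 65% against 35%, two-sided 0.05, 90% power.

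- Uncorrected: n = [1.960·√(2·0.5·0.5) + 1.282·√(0.65·0.35 + 0.35·0.65)]² / 0.30² = (1.386 + 0.864)² / 0.09 = 56.3, so 57.
- Continuity-corrected: (56.3/4)·[1 + √(1 + 4/(56.3·0.30))]² = 62.8, so 63 per group, as stated.
- With 10% drop-out: 126/0.9 = 140, or 70 randomised per arm.

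**3. What the filter does to a comparison.** Let p1 and p2 be the true incidences and f the share that is both treated and attributed, taken as equal in the two arms.

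- Counted risk difference: f·(p1 − p2), so it shrinks in proportion to f.
- Counted risk ratio: f·p1/(f·p2) = p1/p2, so it is unchanged.
- Approximate power, n per arm, p̄ the mean of the two counted rates: Φ{[(p1 − p2)·√n − 1.96·√(2p̄(1 − p̄))] / √(p1(1 − p1) + p2(1 − p2))}, with the counted rates put in.

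Assumed for illustration: p1 = 20%, p2 = 5%, n = 70.

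- f = 1: (0.15·8.367 − 1.96·0.4677)/0.4555 = 0.74, power about 77%.
- f = 0.1: (0.015·8.367 − 1.96·0.1571)/0.1568 = −1.16, power about 12%.

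| Share counted | Expected patients, lidocaine v placebo | Risk difference | Risk ratio | Power |
|---|---|---|---|---|
| 100% | 14.0 v 3.5 | 15 points | 4 | 77% |
| 50% | 7.0 v 1.8 | 7.5 points | 4 | 45% |
| 20% | 2.8 v 0.7 | 3 points | 4 | 20% |
| 10% | 1.4 v 0.4 | 1.5 points | 4 | 12% |

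Range over other assumed rates, all events against a 10% share counted: 30% v 10% goes from about 85% to 13%, and 10% v 2% from about 51% to 9%. The normal approximation is rough at such small counts.

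**The case against.** The strongest case on the other side is that this is a wording problem and no data are lost. Much of it stands.

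- A reader might infer that the trial counts only treated, attributed events. It does not: 5.4 also covers serious events, opiate-related events and digitally recorded vital parameters. A fall in blood pressure is on record whatever its presumed cause.
- A reader might infer that mild signs vanish. Sections 11.6 and 11.9 and the study-sequence table keep them in the record, so a comparison of all adverse events remains possible. Section 5.4 itself names dizziness, ear ringing and skin reactions, which fail to count only when untreated or not attributed.
- Section 11.1 need not restrict collection. Its relatedness clause can attach to serious events alone, and the causality scale in 11.3 has a category for unrelated events, which implies that these are collected.
- The attribution phrase in 5.4 could denote a type of event, namely recognised lidocaine reactions, rather than a case-by-case judgement. A filter of that kind might also remove background noise.
- Infection is a weak example. Section 3.5 says "a higher susceptibility to infection has been discussed", but adds that most studies found sufficient leucocyte function. An infection that prolonged the stay would be serious under 11.2.

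The treatment condition survives every one of these readings. Possible noise reduction supports showing a subset; it does not support making that subset the only defined outcome. That a table of all adverse events could be made is also different from its being planned.

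**Conclusion.** The point holds for the non-serious lidocaine component of the safety outcome. As written, 5.4 leaves untreated mild signs, and events attributed elsewhere, out of the incidence compared between arms. This conflicts with the causality-free definition in 11.2, and no section plans the comparison that the recording in 11.9 would allow.

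The consequence is fewer counted events, a smaller absolute difference and less power to see a harm. Its size is unknown: the documents give neither adverse-event rates nor the share of mild signs that are treated, so every rate in the illustration is an assumption. The equal share in both arms is a further assumption; under it the risk ratio does not move.

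It is tempting to conclude that the arms will look alike. The documents do not support that. It would be a forecast resting on invented rates, and the filter lowers counts without necessarily equalising the arms. Nor does the plan state a safety hypothesis or a power target for safety that the filter would defeat. The change is worth making because it is specific and cheap.

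**What to change.** - **Section 5.4:** define the safety outcome as the number and percentage of patients, by randomised arm, with any adverse event after the start of study drug, whether or not it was treated and whatever its presumed cause. Show severity (11.6), relatedness (11.3) and need for treatment as subsets. Keep serious and opiate-related events as separate lines.
- **Section 11.1:** reword so that the relatedness clause cannot be read as limiting which adverse events are collected, in line with 11.2 and 11.9.
- **Nausea and vomiting:** reconcile their listing in 5.4 as lidocaine adverse events with the exclusion of PONV in the same section, and with their use in 11.6 to define the moderate grade.

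The cost is protocol and CRF wording and somewhat more recording. More background events will be listed in both arms, which the subsets help the reader to sort. No extra visits or patients are needed, because recording of adverse events is already planned at each stage.

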8.7 Trial specific preventive measures

Apart from the study intervention, standard anesthetic technique will be used in all patients at the discretion of the attending anesthesiologist. Medication and treatment plans which are permitted before and/or during the trial include the medication and treatment plans listed in the „Kantonsspital St. Gallen – Standard Anästhesie“. Equipment and medication for resuscitation and treatment of adverse events occurring during and after anaesthetic procedures are available in all operation theatres, the PACU and intensive care unit according to institutional standards. In addition, trained personal is continuous available in these locations. Accordingly, no study specific measures are necessary. Vital parameters (blood pressure, pulse rate, oxygen saturation) will be recorded and possible deviations resulting in clinical relevant consequences treated immediately by attending anesthesiologist. Incidence of any potential AE, SAE due to application of IMPs will be documented and treated (e.g. local skin reactions, nausea, vomiting, dizziness, ear ringing, cardiac arrhythmia with relevant hemodynamic outcome or cardiac arrest) or adverse events related to opiates (e.g. hypoventilation).

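### The SAE part of the safety outcome in 5.4 names only two cardiac events, which does not match 8.7, 11.2 and 11.6 and carries over into the reporting rule in 11.7

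*Combined protocol and SAP*

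**What the plan says.** Section 5.4 sets out the event part of the safety outcome in one sentence with three limbs.

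- AEs attributed to lidocaine that need treatment, with an open list: "e.g. local skin reactions, nausea, vomiting, dizziness, ear ringing, etc".
- "serious adverse events (SAE) (cardiac arrhythmia with relevant hemodynamic outcome, cardiac arrest". The bracket closes there, with no sign that these are examples.
- Opiate-related events, with a bracket naming respiratory events and ileus, also without such a sign.

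Other sections describe serious events more broadly. Under 11.2 an SAE "is classified as any untoward medical occurrence that" meets any one of the usual seriousness criteria, for example that it "requires in-patient hospitalization or prolongation of existing hospitalization"; important medical events are added. Section 11.6 has the category "Severe: drowsiness confusion, muscle twitching, convulsions, loss of consciousness, cardiac arrhythmias with hemodynamic instability, cardiac arrest" and brings such reactions, when due to the study drug, within the SAE definition. Section 8.7, on documenting and treating events, uses one list of examples for AEs and SAEs together: "e.g. local skin reactions, nausea, vomiting, dizziness, ear ringing, cardiac arrhythmia with relevant hemodynamic outcome or cardiac arrest". Section 3.5 gives the order of signs once toxic plasma levels are reached: "neurological and central nervous stimulation become apparent, followed by inotropic and bathmotropic effect-related cardiac failure".

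On analysis, 10.4 names the two arms and the whole population, and 10.5 covers primary and secondary endpoints. Neither mentions safety. Sections 11.1 and 11.9 provide for the collection of SAEs; 11.1 adds a qualifier about relation to the study drug.

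On reporting, 8.5 has the Principal Investigator told of an SAE within 24 hours, and 9.3 has drug-related SAEs reported to the Sponsor Investigator within 24 hours. Section 11.7 has primary, secondary and safety events recorded on the CRF but not reported as SAEs unless judged exceptional. It sends events outside those outcomes to the Sponsor Investigator within 24 hours.

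**The concern.** Section 5.4 is where the plan names safety incidences as outcomes. With no safety analysis in section 10, it is also the main guide to what will be reported. If its SAE limb is taken at its word, the reported SAE incidence is an incidence of two cardiac events. Readers would take it for the incidence of SAEs in the sense of 11.2 and 11.6. By 3.5's own account, cardiac failure follows central nervous signs, so the limb names the later stage of toxicity only.

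Whether the bracket is a definition or a set of examples would be settled when the report is written, after the data are known. Because 11.7 ties its exemption to membership of the safety outcomes, the same uncertainty also affects how some SAEs are reported during the trial.

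**Working it through.** No calculation in the plan depends on this point, so the check is a comparison of the sections.

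**Step 1: overlap of 5.4 with 11.6.** Taking drowsiness and confusion as one item, as the text prints them, 11.6 lists six groups: drowsiness/confusion, muscle twitching, convulsions, loss of consciousness, haemodynamically unstable arrhythmia and cardiac arrest. The SAE limb of 5.4 names the last two. That is 2 of 6; the other four are nervous system events.

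**Step 2: where each kind of SAE falls if 5.4 is read literally.**

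| Event | SAE under | Place in 5.4 |
|---|---|---|
| Haemodynamically relevant arrhythmia or cardiac arrest due to the study drug | 11.6 | SAE limb |
| Convulsion attributed to lidocaine, treated | 11.6 | AE limb only |
| Severe reaction in 11.6, non-cardiac, attributed to lidocaine, no treatment needed | 11.6 | None, because the AE limb requires treatment |
| Opiate-related respiratory event meeting a seriousness criterion | 11.2 | Opiate limb |
| Non-cardiac SAE attributed to neither drug class, e.g. a surgical complication that prolongs the stay | 11.2 | None |

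**Step 3: consequence under 11.7.**

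- Cardiac arrest is in 5.4 on any reading. Section 11.7 therefore exempts it from SAE reporting unless exceptional, while 8.5, and 9.3 if it is drug-related, require notice within 24 hours. This conflict does not depend on how the bracket is read.
- A treated convulsion attributed to lidocaine is a safety outcome on either reading, through the AE limb, and meets the same conflict.
- A non-cardiac SAE attributed to neither drug class changes route. If the bracket is a definition, the event lies outside the safety outcomes and goes to the Sponsor Investigator within 24 hours. If the bracket gives examples, the event becomes a safety outcome and falls under the exemption.

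Section 11.7 is also inconsistent within itself. One sentence takes safety outcomes out of the SAE definition when they are judged exceptional; the next exempts them from SAE reporting unless they are judged exceptional.

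**Step 4: what a reported zero would mean (illustration).** From 10.3, 63 per group gives 126, and 126/0.9 = 140, the plan's total. At 1:1 (6.3) that is 70 per arm. With no event among 70, the upper limit is 1 − 0.05^(1/70) = 4.2% (one-sided 95%), or 1 − 0.025^(1/70) = 5.1% (upper end of the two-sided 95% interval). These bounds hold for any kind of event. They apply only to what was counted, so a zero in the 5.4 SAE limb would bound the two cardiac events and no other SAE.

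**The case against.** The best defence is that the bracket was never meant as a definition. Section 5.4 says neither 'only' nor 'defined as'. Section 8.7 lists the same cardiac events as examples. The author marks examples inconsistently: the opiate bracket in 5.4 has no marker, while its counterpart in 8.7 has one. Section 9.3 refers to drug-related SAEs without restriction to an organ system. SAEs are defined broadly in 11.2 and 11.6 and collected under 11.1 and 11.9, so a full table could be drawn up at any time. This much stands: a closed list is an inference, and the events are not lost. But the inference is a natural one beside the open AE list, 8.7 deals with documentation and treatment and does not define outcomes, and collecting events does not commit anyone to reporting them by arm.

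Some stronger readings are tempting and do not hold.

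- A reader might infer that a planned comparison of the arms excludes non-cardiac SAEs. Section 10 defines no safety comparison for any event, so nothing is excluded from one.
- A reader might infer that central nervous SAEs would not be counted at all. Those attributed to lidocaine and treated fall in the open AE limb of 5.4.
- A reader might infer that central nervous toxicity is the chief serious harm to expect. Section 3.5 gives only the order of signs at toxic levels. Section 3.2 reports no evidence of a higher risk of intoxication, arrhythmia or death, and 3.5 cites a comparable incidence of adverse effects with placebo.
- The documents give no rate for central nervous SAEs, so the number likely to be missed cannot be estimated.

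**Conclusion.** The point holds as a mismatch between sections, with consequences for the reported outcome and for reporting during the trial. The SAE limb of 5.4 is narrower than 11.2 and 11.6 and at odds with the examples in 8.7. On the literal reading it covers 2 of the 6 groups of severe reactions in 11.6, moves treated non-cardiac SAEs attributed to lidocaine into the AE count, and has no place for SAEs attributed to neither lidocaine nor opiates. Section 10 does not make up for this, because it plans no safety table by arm.

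The conflict between 11.7 and the 24-hour rules in 8.5 and 9.3 exists on either reading. What the bracket decides is how many further SAEs the exemption reaches. The consequences for the SAE count assume the literal reading, which the text allows but does not impose. The point says nothing about how often such events will occur, and it does not show that the trial would wrongly report lidocaine as safe.

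**What to change.** Three changes, to be made together:

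1. In 5.4, replace the bracket after the SAE term with: *all SAEs as defined in 11.2 and 11.6, e.g. cardiac arrhythmia with haemodynamic consequences, cardiac arrest, convulsions*. Both sections must be cited: drowsiness or muscle twitching is an SAE under 11.6 when due to the study drug but need not meet 11.2.
2. In section 10, add a table by arm of the number of patients with at least one SAE, with rows for central nervous, cardiac and other events. State that patients withdrawn because of an SAE stay in this table, since 7.5 (such SAEs are grounds for withdrawal) and 10.8 (data of drop-outs are disregarded) could be read together to remove them.
3. Reconcile 11.7 with 8.5 and 9.3, so that listing an event as a safety outcome does not take an SAE out of 24-hour reporting, and resolve the two opposed sentences in 11.7. Without this step, the first change would extend the exemption to every SAE.

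The cost is editing in 5.4, section 10 and 11.7, plus one more table. The collection rules in 11.1 and 11.9 already provide the data. The downside is that reported SAE counts may be higher.
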